P-values ≥ 0.0001 will be reported to 4 decimal places; p-values less than 0.0001 will be reported as " <0.0001 ". The mean, standard deviation, and any other statistics other than quantiles, will be reported to one decimal place greater than the original data. Quantiles, such as median, minimum, or maximum will use the same number of decimal places as the original data. Estimated parameters, not on the same scale as raw observations (e.g. regression coefficients) will be reported to 3 significant figures.

Adherence to interventions

Analysis of both intention-to-treat (ITT) and as-treated populations will be performed. All participants who are randomized to a trial arm will be included in the ITT analyses. Participants who adhere to major engagement criteria for their primary intervention will be included in the as-treated analyses.

Analysis methodology

Aim 1

To compare the impact of two interventions delivered online: 1) a dialogue-based webinar (webinar) using the existing COVID-19 Option Grid conversation aid and, 2) an interactive and, dynamic, and multi-component social media web application (social media website), compared to enhanced usual practice (link to Centers for Disease Control (CDC) vaccine website), on COVID-19 vaccine confidence (primary outcome), and other secondary outcomes among LTCWs. We hypothesize that each intervention will be superior to enhanced usual practice at increasing vaccine confidence (*Hypothesis 1.1*) and that the dialogue-based webinar intervention will be superior to the social media arm at increasing vaccine confidence (*Hypothesis 1.2*).

Corresponding analyses

Primary outcome

The primary outcome is the binary classifier of vaccine confidence derived from the three-item Vaccine Confidence Index (VCI), evaluated at 3 weeks post-randomization, which will be analyzed by randomization arm. The determined binary predictors of intervention outcomes will be compared using two-proportion z-tests to identify significant differences between each intervention and enhanced usual practice (Arm 1 vs Arm 3 & Arm 2 vs Arm 3 - superiority analyses) and between the intervention arms (Arm 1 vs Arm 2 - two-tailed equivalency analysis).

Secondary outcomes

- *Change from baseline in COVID-19 Vaccine Confidence.* Analysis of change from

baseline will be based on a binary classifier whether the average score increases (1) or does not increase (2) at T1, T2, and T3 versus baseline.

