The primary outcome involves three separate tests, one a two-tailed equivalence test and two one-tailed superiority tests. In order to achieve a family-wise error rate less than 0.050, the Bonferroni method was employed to set a p-value threshold at 0.016 for each of the three primary outcome analyses. For each comparison, mean-value separation will be considered significant based on a 98.4% confidence interval, which translates to +/- 2.45 times the standard

error for the sample mean for the equivalence test and greater than 2.15 times the standard error for the superiority analyses.

Based on the high number of secondary outcome analyses (cross-sectional T1; change from baseline; ITT; as-treated), results data for these outcomes will be viewed in more aggregate form as trending in one direction or not, rather than adopting a specific Bonferroni-corrected p-value threshold.

References

1. B. Rocks, Interval Estimation for the “Net Promoter Score.” *Am. Stat.* 70, 365–372 (2016).
2. R. M. Baron, D. A. Kenny, The moderator–mediator variable distinction in social psychological research: Conceptual, strategic, and statistical considerations. *J. Pers. Soc. Psychol.* 51, 1173–1182 (1986).
3. T.E. Raghunathan, J.M. Lepkowski, J. Van Hoewyk, P. Solenberger, et al. A multivariate technique for multiply imputing missing values using a sequence of regression models. *Surv. Methodol.* 27, 85–96 (2001).

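### The SAP's multiplier sentence names the standard error of a sample mean for Arm 1 vs Arm 2 and none in particular for the superiority tests; it should name the standard error of the difference used by the planned z-tests

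*Combined protocol and SAP*

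**What the plan says.** Appendix B, under the Aim 1 primary outcome, defines a binary endpoint: "The primary outcome is the binary classifier of vaccine confidence derived from the three-item Vaccine Confidence Index (VCI), evaluated at 3 weeks post-randomization". The arms "will be compared using two-proportion z-tests to identify significant differences between each intervention and enhanced usual practice", and the same sentence covers Arm 1 vs Arm 2.

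The Multiple testing paragraph describes the family as "one a two-tailed equivalence test and two one-tailed superiority tests". Its aim is stated as "In order to achieve a family-wise error rate less than 0.050", and for this "the Bonferroni method was employed to set a p-value threshold at 0.016 for each of the three primary outcome analyses".

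The next sentence turns the threshold into multiples of a standard error. It begins "mean-value separation will be considered significant based on a 98.4% confidence interval, which translates to +/- 2.45 times the standard" and continues "error for the sample mean for the equivalence test and greater than 2.15 times the standard error for the superiority analyses". The reference to a sample mean belongs grammatically to the Arm 1 vs Arm 2 clause only. The superiority clause mentions a standard error without saying of what. The documents give no formula for either.

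**The concern.** A gap between two arms has to be judged against the standard error of that gap. With 1:1:1 allocation (protocol, Allocation of Interventions) and no true difference, this is √2 ≈ 1.41 times the standard error of one arm's mean. Multiplying 2.45 by the smaller quantity sets the bar for Arm 1 vs Arm 2 too low.

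The sentence is phrased as a decision rule for each comparison, so it could be programmed as it stands. Two analysts working from the same appendix, one from the named test and one from the multiplier sentence, could then reach opposite verdicts on a primary comparison.

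**Working it through.** **Inputs.** From Appendix B, Multiple testing: threshold 0.016 per test, multipliers 2.45 (two-tailed) and 2.15 (one-tailed), family-wise limit 0.050. From the protocol's sample size section: 600 per arm, or 360 after 40% attrition, and a planned difference of 8 points. Φ is the standard normal distribution function.

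**1. The stated multipliers.** 0.05/3 = 0.0167, which the plan takes down to 0.016. The normal critical values for 0.016 are 2.409 two-sided and 2.144 one-sided.
- 2.15 agrees closely: 1 − Φ(2.15) = 0.0158.
- 2.45 does not: 2 × [1 − Φ(2.45)] = 0.0143. Using 0.05/3 gives 2.394, so it does not explain 2.45 either. This slip is conservative.

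**2. Multipliers applied to the standard error of the difference (the z-test).** The error rates are 0.0143 for Arm 1 vs Arm 2 and 0.0158 for each superiority test. Bonferroni sum: 0.0143 + 2 × 0.0158 ≈ 0.046. Simulated family-wise error with three equal arms, no true differences and normal statistics: 0.0406 in 4 million trials, and 0.0404 in a repeat with 8 million. The limit of 0.050 is held.

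**3. The sentence as written.** The difference is compared with 2.45 × SE(one arm). Because SE(difference) = √2 × SE(one arm), the effective critical value is 2.45/√2 = 1.732, and 2 × [1 − Φ(1.732)] = 0.083.
- *Sample mean taken for Arm 1 vs Arm 2 only:* Bonferroni sum 0.0832 + 2 × 0.0158 ≈ 0.115; simulated family-wise error 0.103.
- *Same standard error also used for superiority:* 2.15/√2 = 1.520 and 1 − Φ(1.520) = 0.064 per test; sum 0.0832 + 2 × 0.0642 ≈ 0.212; simulated family-wise error 0.169.

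These tail areas do not depend on the confidence rate. Binomial simulation at assumed rates of 30% and 50%, with 600 and 360 per arm, agrees. With one arm's standard error the two-sided error is 0.080 to 0.087. With the pooled standard error of the difference it is 0.014 to 0.015.

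**4. What this means in percentage points.** The documents give no base rate, so a range is assumed. For Arm 1 vs Arm 2 with 600 per arm:

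| Assumed rate | SE, one arm | SE, difference | 2.45 × SE, one arm | 2.45 × SE, difference |
|---|---|---|---|---|
| 30% | 0.0187 | 0.0265 | 4.6 points | 6.5 points |
| 50% | 0.0204 | 0.0289 | 5.0 points | 7.1 points |

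Here SE(one arm) = √[p(1 − p)/600]. With 360 per arm the cuts are 5.9 to 6.5 points against 8.4 to 9.1. The planned difference is 8 points, so an observed gap that falls between the two cuts is plausible.

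**The case against.** The strongest reply is that the plan already holds a complete and valid rule without this sentence. Appendix B names the two-proportion z-test, which divides the difference by the standard error of the difference, and the p-value threshold of 0.016 stands one sentence before the multipliers. The multipliers can be read as a gloss on that threshold, and 2.15 is evidently a normal quantile for 0.016. An analyst who runs the named test gets the right standard error automatically, and the statistician on the monitoring board is to replicate the primary analyses.

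Most of this stands. It disposes of three stronger conclusions that a reader might draw:
- *That the primary analysis fails to control error.* On the named test and threshold it does control it (step 2). The multiplier sentence is not the only place that yields a verdict.
- *That family-wise error is about 17%.* This requires carrying the sample mean into the superiority clause, which does not contain it.
- *That significance means two arm-specific intervals must not overlap.* The text says nothing of overlap. It refers to a confidence interval for each comparison, which points to one interval for the difference.

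The reply does not make the sentence correct. The sentence says when a comparison is to be called significant, and for Arm 1 vs Arm 2 it names a quantity that contradicts the test named earlier. Even the narrowest literal reading, with only that comparison affected, exceeds the paragraph's own limit. Replication exposes a discrepancy but does not say which text governs.

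**Conclusion.** The wording is wrong for Arm 1 vs Arm 2 and incomplete for the two superiority tests. The intended analysis is probably sound. Under the z-tests at 0.016, family-wise error is about 0.04. Applied literally, the sentence tests Arm 1 vs Arm 2 at about 8.3% instead of 1.6%, and family-wise error is about 0.10, or about 0.17 if one arm's standard error is used throughout. The inflation is conditional on that literal use, and nothing in the documents shows that it is intended.

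The error rates assume equal arms, no true differences and the normal approximation. The percentage-point cuts also assume confidence rates of 30% to 50%. Arm 1 vs Arm 2 is treated as the two-tailed z-test that the plan describes; whether equivalence is the right label for it is a separate matter. This should be corrected before analysis, because it concerns the primary verdict and the correction is simple.

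**What to change.** Replace the multiplier sentence in Appendix B, Multiple testing, with wording to this effect: for each primary comparison, the difference in proportions is divided by the standard error of that difference, as in the two-proportion z-test named for the primary outcome, and compared with the critical value for 0.016, which is 2.41 two-sided for Arm 1 vs Arm 2 and 2.14 one-sided for each superiority test (2.409 and 2.144 to three decimals).

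In the same edit:
- delete the reference to the sample mean;
- state whether the standard error is pooled or unpooled, which the plan does not currently choose;
- say that the 98.4% interval is for the difference: two-sided for Arm 1 vs Arm 2, and a one-sided bound for the superiority tests;
- correct 2.45 to 2.41.

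With critical values 2.409 and 2.144 on the standard error of the difference, simulated family-wise error is 0.042, still below 0.050. The cost is SAP wording only, with no change to data, sample size or design.
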